**Site Record Retention Policy [21 CFR 812.140 (D)]**

The sponsor and clinical site will maintain all records pertaining to this study for a period of two years following: the date on which the investigation is terminated or completed, or the date that the records are no longer required for purposes of supporting a pre-market approval application. Record retention dates will be provided to all concerned by the sponsor.

**Informed Consent & Institutional Review Board/Ethic Committee [21 CFR Parts 50 & 56]**

All subjects must provide written informed consent in accordance with the local clinical site's IRB. A copy of the consent form from each center must be forwarded to the Sponsor for review and approval prior to submitting it to the IRB. The site must provide the Sponsor with a copy of the clinical site's IRB approval letter and the informed consent. Yearly approvals for the continuation of the Study at each clinical site must also be forwarded to the Sponsor.

All Protected Health Information (PHI) to be collected in the study will be described in the informed consent form, and all study data will be managed in accordance with the Privacy Law (HIPAA).

The electronic version of this document is stored in Agile PLM and is considered the controlled copy.

Printed copies are for reference only and considered UNCONTROLLED.

CONFIDENTIAL AND PROPRIETARY OF AURIS HEALTH, INC.

# 1 Introduction

This is the Statistical Analysis Plan (SAP) for the final analysis of data collected under Protocol 2023-URO-0001. This SAP describes in detail the statistical methodology and statistical analyses for this protocol.

## 1.1 Study Objectives

The aim of the study is to assess the successful completion of robotic mini-Percutaneous Nephrolithotomy (PCNL) using the MONARCH™ Platform, Urology. This study will also assess stone clearance (Post-Operative Day 30) and the safety profile following this procedure.

## 1.2 Study Design

This is a prospective, single arm observational multicenter study to collect outcomes data on the robotic-assisted mini-PCNL removal of kidney stones using the MONARCH™ Platform, Urology system.

The study originally intended to enroll up to 60 subjects across up to 3 sites. Each enrolled subject will be followed up to 90 days  $\pm$  14 days post procedure. Enrollment was stopped prior to reaching the original maximum of 60 subjects for business reasons that were unrelated to subject safety.

# 2 Treatment Assignment

This is a single-arm study where all enrolled subjects will have the MONARCH™ system utilized for removal of kidney stones via a mini-PCNL procedure.

# 3 Randomization and Blinding Procedures

As this is a single-arm study, no randomization occurred, and no blinding procedures were required.

# 4 Interval Windows

Interval windows for the purpose of analysis in this study are not defined outside of those already specified in the protocol for visit scheduling where the collection of data for the primary and safety endpoints occurs.

Table 1 Schedule of Assessments in the protocol specifies the following visits and windows where applicable:

- Screening/baseline: completed not more than 120 days prior to the procedure
- Procedure Day
- Follow-Up, Day 1
- Post-operative 30-day follow-up ( $\pm$  7 days)

- Post-operative 90-day follow-up ( $\pm$  14 days)

Any information entered in the electronic Case Report Forms (eCRFs) at a given visit will correspond to the scheduled visit. There will be no assigning of observations to time points outside of the visit to which they are recorded in the eCRFs.

## 5 Levels of Significance

No hypotheses were specified for this study and no p-values are being calculated, therefore no level of significance is specified. All estimation of endpoints will be performed using 95% confidence intervals where indicated below.

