## 2. Introduction

The current standard of care treatments for kidney stones include Extracorporeal delivery of Shock Waves for Lithotripsy (commonly referred to as ESWL, which is trademark of Dornier MedTech), flexible Ureteroscopy (URS), and Percutaneous Nephrolithotomy (PCNL). Each of these approaches present challenges for achieving a stone free state in the kidney, especially for patients with mild to moderate stone burden.

The performance of the MONARCH™ Platform, Urology in a clinical setting is still being established. The MONARCH™ system facilitates a minimally invasive, robotically-assisted hybrid (retrograde and antegrade access) mini-PCNL procedure that can performed by a single qualified professional. The initial clinical experience (up to 20 subjects at a single site, with cases performed across 2 endourologist operators) focused on procedural completion and initial clinical safety data. This study continues to assess these outcomes following MONARCH™ mini-PCNL, but at additional hospital sites and with additional endourologist operators. Furthermore, this study also expands the assessment of post-operative outcomes. Specifically, this study also intends to estimate the Day 30 post-operative stone clearance following mini-PCNL using the MONARCH™ system. Additional post-operative outcomes will also be explored to differentiate MONARCH™ from standard-of-care treatment modalities. One exploratory outcome will be the immediate post-operative (Day 1) stone clearance following MONARCH™ mini-PCNL. This device allows for a continuous removal of stone fragments, as these fragments are created while lasing the primary stone. It is possible, that this may confer advantages in increasing clearance efficiency intraoperatively and thereby provide immediate clearance of stones. Accordingly, this study intends to explore immediate post-operative stone clearance (Day 1) in conjunction with the conventional assessment timed at 30 days. Another exploratory outcome will be patient-reported outcomes on quality of life following mini-PCNL with the MONARCH™ system. Finally, data collected from this study will be used to optimize the robotic platform.

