### 8.2 Levels of Significance

No hypotheses are specified for this study and no p-values are being calculated, therefore no level of significance is specified. All estimation of endpoints will be performed using 95% confidence intervals.

The electronic version of this document is stored in Agile PLM and is considered the controlled copy.

Printed copies are for reference only and considered UNCONTROLLED.

CONFIDENTIAL AND PROPRIETARY OF AURIS HEALTH, INC.

	PROTOCOL	Doc #:	104-016667-00
	Monarch Uro - Post-Operative Outcomes Study (2023-URO-0001)	Rev:	C
		Page:	30 of 52

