### 8.5 Analyses to be Conducted

Categorical variables will be summarized descriptively by frequencies and associated percentages. Continuous variables will be summarized descriptively by number, mean, standard deviation, median, minimum, and maximum. Confidence intervals will also be provided for procedure-related variables. Demographic data will be summarized at the subject level, whereas procedure-related data (including patient-reported outcomes) will be summarized at the procedure level. Any deviations from this general approach will be detailed in the SAP.

Subject disposition will be summarized in total using counts and percentages. The number and percentage of subjects completed and discontinued will be tabulated along with the specific reasons for discontinuation. Subject demographics and surgical characteristics will be summarized.

The number and percentage of procedures achieving successful completion of the robotic-assisted kidney stone removal procedure will be summarized and an exact 95% confidence interval will be estimated.

The number and percentage of procedures resulting in a subject who is determined to be stone free at Day 30 will be summarized and a 95% confidence interval will be estimated. Similar analyses will be performed for the stone-free rate at Day 1. Patient reported outcomes will be analyzed with methodology consistent to the recommendations of the published outcome measure.

All device-related and procedure-related AEs reported during the study will be coded to the Medical Dictionary for Regulatory Activities (MedDRA). All AEs will be summarized by MedDRA system organ class and preferred term by procedure group and in total. Separate summaries will be provided for device-related and procedure-related AEs. Serious AEs will be summarized in a similar manner. Separate summaries by system organ class and preferred term may be provided for events classified as major (Clavien-Dindo Class III or higher) and minor (Clavien-Dindo Class I or II). Separate summaries by Clavien-Dindo grade will be summarized.

Summary statistics will be provided for additional exploratory data points collected in this study. All summaries will be performed only on subjects undergoing the scheduled procedure and only observed data will be summarized. There will be no imputation of data for early terminated subjects or for missing data within the database.

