Interim analysis of device safety events will be conducted from the first 20 patients undergoing the study procedure, which is inclusive of this study and a prior clinical study, Initial Experience of the Treatment of Kidney Stones with the MONARCH™ Platform, Urology (104-010990-00). Interim analyses may be conducted to support additional business needs (e.g., abstract submission to scientific conference). Data will also be summarized upon study completion.

The electronic version of this document is stored in Agile PLM and is considered the controlled copy.

Printed copies are for reference only and considered UNCONTROLLED.

CONFIDENTIAL AND PROPRIETARY OF AURIS HEALTH, INC.

 AURIS	PROTOCOL	Doc #:	104-016667-00
	Monarch Uro - Post-Operative Outcomes Study (2023-URO-0001)	Rev:	C
		Page:	31 of 52

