## 8.6 Secondary Endpoints and Associated Hypotheses

The following secondary endpoints are specified for this study:

- Stone free rate ( $\leq 4$  mm residual fragments, measured 30-days post-operative)
- Adverse events through 90-days post-operative, scored on the Clavien-Dindo scale
- Conversion to conventional treatment methods due to study device-related safety event

No associated hypotheses are specified.

The stone free rate will be computed as the percentage of patients who are stone free assessed by computed-tomography (CT) scan at post-operative Day 30. Stone free is defined as having  $\leq 4$  mm residual cumulative stone burden detected by CT. Patients who are found to not have any residual stone fragments at Day 1, will not undergo a second CT at post-operative Day 30, and will be presumed to be stone free at Day 30 for this calculation. The number and percentage of procedures resulting in a subject who is determined to be stone free at Day 30 will be

summarized and a 95% confidence interval will be estimated. Similar analyses will be performed for the stone-free rate at Day 1.

All adverse events will be captured up to post-operative Day 90, at which point the subject exits the study. Summaries will be provided for all adverse events by MedDRA System Organ Class and Preferred Term. Similar summaries will be provided for device-related AEs, procedure-related AEs, serious adverse events (SAEs), device-related SAEs, and procedure-related SAEs. Adverse events will also be scored on the Clavien-Dindo scale and summaries will be provided by System Organ Class and Preferred Term for events that are graded at III or higher on the Clavien-Dindo scale and then similarly for those that are Grade II or lower in a separate output table.

The number and percentage of procedures converted to conventional stone removal procedures (e.g., ureteroscopy or percutaneous nephrolithotomy) due to the occurrence of a study device-related safety event will be summarized. A qualifying safety event is a study device-related adverse event that occurs during the study procedure that prompts the physician to abort the study procedure and pursue a conventional stone removal procedure.

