## 8.9 Plans for Interim Analysis

No interim analysis was planned for this study that had the intention of altering study design or execution. Three summaries of data were provided to support abstract writing that described the initial experiences of the device use in subjects at the respective sites.

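### The SAP gives the device-related conversion endpoint no confidence interval and omits the by-grade Clavien-Dindo summary, both of which the protocol promises, and records neither as a change

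*SAP*

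**What the plan says.** **Intervals.** Protocol 8.2 states without qualification: "All estimation of endpoints will be performed using 95% confidence intervals". Protocol 8.5 adds: "Confidence intervals will also be provided for procedure-related variables". SAP 5 repeats the first sentence with a limit: "All estimation of endpoints will be performed using 95% confidence intervals where indicated below". SAP 8.5 then gives an exact interval for procedure completion. SAP 8.6 gives a 95% interval, method unnamed, for the stone-free rate at Day 30 and, by reference, at Day 1. For conversion caused by a device-related safety event, SAP 8.6 specifies only this: "The number and percentage of procedures converted to conventional stone removal procedures". Adverse events are tabulated by system organ class and preferred term, with no interval.

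**Clavien-Dindo.** Protocol 8.5 makes a major/minor split optional and then commits to more: "Separate summaries by Clavien-Dindo grade will be summarized". SAP 8.6 provides the split (III or higher, II or lower) and no table by grade.

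**First-20 look.** Protocol 8.5: "Interim analysis of device safety events will be conducted from the first 20 patients undergoing the study procedure, which is inclusive of this study" and an earlier study of the device. SAP 8.9: "No interim analysis was planned for this study that had the intention of altering study design or execution". It then lists three data summaries, all made for abstracts, and does not mention the first-20 look.

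**Departures.** Protocol 8.5 says that deviations from its general approach will be set out in the SAP. The SAP presents none of these differences as a deviation.

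**The concern.** Two of the three secondary endpoints concern safety: device-related conversion, and adverse events graded on the Clavien-Dindo scale. These are the results for which the SAP provides no measure of precision. The study is small and enrollment stopped before the planned maximum, so very few conversions, perhaps none, may be seen. A table reading 0 (0%) does not show how large a rate the data still allow.

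The grading matters for another reason. Grade is what the adverse-event endpoint is scored on. With two bands, an intervention without general anesthesia (IIIa) and a death (V) fall in the same band, and the tables cannot separate them.

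The first-20 look is a question of reconciliation. The protocol says it will be done, and the SAP section on interim analyses does not account for it.

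**Working it through.** **1. Protocol against SAP**

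| Item | Protocol | SAP |
|---|---|---|
| Completion (primary) | 8.5: exact 95% interval | 8.5: exact 95% interval |
| Stone-free rate | 8.5: 95% interval, method unnamed | 8.6: same |
| Device-related conversion | 8.2 (general) and 8.5 (procedure-related variables): interval | 8.6: number and percentage, no interval |
| Adverse events | 8.2 (general) only; the adverse-event paragraph of 8.5 names no interval | 8.6: no interval |
| Clavien-Dindo by grade | 8.5: firm | absent |
| Clavien-Dindo major/minor | 8.5: optional | 8.6: present |
| First-20 device-safety look | 8.5: firm | 8.9: not mentioned |

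**2. Inputs for the arithmetic.** The planned maximum is 60 subjects (Protocol synopsis and 8). SAP 1.2 says enrollment stopped below 60 and gives no number, so n = 40, 30 and 20 are assumed values. Neither document derives a precision or power figure (Protocol 8.4, SAP 7), so there is none to reproduce.

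**3. Upper limit with zero events.** The exact (Clopper-Pearson) two-sided 95% upper limit for 0/n is 1 − 0.025^(1/n).

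- n = 60: 1 − 0.025^(1/60) = 0.0596, or 6.0%
- n = 40: 0.0881, or 8.8%
- n = 30: 0.1157, or 11.6%
- n = 20: 0.1684, or 16.8%

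With one event the exact upper limits are 8.9% at n = 60, 13.2% at 40 and 24.9% at 20.

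**4. Chance of seeing zero when the true rate is not zero.** P(0 events) = (1 − p)^n.

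- p = 5%: 0.046 at n = 60, 0.129 at 40, 0.358 at 20
- p = 2%: 0.298 at n = 60, 0.446 at 40, 0.668 at 20

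**5. Why the stone-free method should be named.** The Wald interval is p̂ ± 1.96 × √(p̂(1 − p̂)/n). At p̂ = 1 the square root is 0 and the interval has no width. For 30/30 the exact lower limit is 0.025^(1/30) = 0.884, or 88.4%. Neither document specifies Wald; the SAP leaves the choice open.

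**6. Make-up of the first-20 look.** Protocol 2 describes "The initial clinical experience (up to 20 subjects at a single site, with cases performed across 2 endourologist operators"). I read this as the earlier study named in Protocol 8.5. If it supplied k of the 20 pooled patients, with k at most 20, this study supplied 20 − k, which could be as few as 20 − 20 = 0. The documents do not give k.

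**The case against.** The strongest reply is that Protocol 8.5 goes through the endpoints one by one, naming an interval for completion and for stone-free rate and none for adverse events, and that SAP 8.5 and 8.6 follow it. On this reading, Protocol 8.2 only fixes the level at 95% wherever an interval is given. Protocol 6 also defines conversion simply as a number of procedures.

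Part of this stands. For adverse events the commitment rests on the general sentence in 8.2 alone, and tabulation by system organ class and preferred term is not plainly estimation. For conversion the commitment is firmer. It is a named endpoint measured per procedure, so the 8.5 sentence on procedure-related variables applies as well as 8.2.

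On grading, Appendix III allows seven grades to be contracted to five, so the a/b subclasses are optional. It does not offer contraction to two. SAP 8.1 promises per-subject listings of all eCRF data, so grades should be recoverable if recorded there, but a listing is not the promised summary.

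Four stronger readings are tempting and are not supported:

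- **That safety results are bare counts.** SAP 8.1 and 8.6 give percentages, and a reader with the denominator could work out the limit.
- **That the plan treats a zero count as zero risk.** No such claim appears. The difficulty with a zero count comes only from the missing intervals; neither a by-grade table nor an interim look would put a bound on it.
- **That the first-20 look was dropped.** The SAP covers the final analysis, and 8.9 denies only analyses meant to alter design or execution. Whether the look took place is not stated.
- **That there was no safety oversight, because SAP 9 reports no monitoring committee.** The protocol provides for medical-monitor review of adverse events, 24-hour reporting of serious events and termination criteria.

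**Conclusion.** Two departures from the protocol are established: no interval for device-related conversion, and no summary by Clavien-Dindo grade. Neither is disclosed as a change. The absence of intervals for adverse events is a weaker departure, resting on Protocol 8.2 alone. The first-20 look is unaccounted for in SAP 8.9, and nothing more can be said from the documents.

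A result of zero conversions would be compatible with a true rate of up to 6.0% at n = 60, and up to 16.8% if n were as low as 20. These limits assume one procedure per subject, or independent procedures. Protocol 3.2 lets a subject have both kidneys treated, so the number of procedures may exceed the number of subjects. With one procedure per subject, precision is worse than at n = 60, because fewer than 60 were enrolled. The point should be corrected before the final analysis. It affects what the study can conclude on safety, and it does not touch the primary endpoint.

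**What to change.** In SAP 8.6:

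- Add an exact (Clopper-Pearson) 95% interval for device-related conversion, with the procedure as the unit. State how many subjects contribute two procedures.
- Add an exact 95% interval for the proportion of subjects with any Clavien-Dindo grade III or higher event.
- Name the exact method for the stone-free rate at Day 30 and Day 1.
- Add a summary by grade, I to V, with the a/b subclasses if they are recorded.

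If any of these is deliberately left out, record it in the SAP as a deviation from Protocol 8.2 or 8.5, with the reason.

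In SAP 8.9, state whether the first-20 device-safety look was done and how many patients came from each study, or record its removal. A new summary of this study's own first 20 patients is not needed: the protocol does not call for one, and it would serve no monitoring purpose now that enrollment has stopped.

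The cost is SAP wording, a few table columns and one additional table. No new data are needed.

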## 6 Analysis Sets

The summary of all performance and safety endpoints will be performed on the set of subjects in whom the MONARCH™ system is utilized during the procedure. This will be labeled as the Full Analysis Set (FAS) and will be identified by having a time recorded in the “When was the Ureteroscope introduced (timestamp)?” field on the Procedure: Ureteroscopy and Percutaneous Access eCRF.

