#### Description of the study procedure: Mini-PCNL

This robotically enabled hybrid procedure called the MONARCH™ Mini-PCNL will allow the clinician to obtain retrograde and percutaneous access to patient's kidney under continuous visualization for therapeutic applications (i.e., stone removal). The aim of the study is to evaluate clinical safety and procedural effectiveness of the robotic-assisted diagnostic and therapeutic procedures performed with the MONARCH™ Platform – Urology. The procedure includes the following components.

*Retrograde Access:* The user gains retrograde access to the kidney via conventional cystoscopy techniques and places a ureteral access sheath to maintain access to the kidney.

*Ureteroscopic Surveillance:* The user manually inserts and navigates the ureteroscope to the kidney under direct endoscopic visualization. Once the user confirms access to the kidney, the ureteroscope is docked to the arm. The physician can command insertion/retraction, articulation, and roll of the ureteroscope via the MONARCH™ Controller to survey the kidney and locate the stone.

*Percutaneous Access:* The use of electromagnetic (EM) sensing capabilities provides a rendezvous point with the ureteroscope to guide the advancement of the needle into the kidney under direct visualization and control by the physician. The EM field generator and mount are present on the electromechanical arm by the patient's flank to create the EM field. The user determines which calyx to access and parks the ureteroscope in this calyx. The system creates a virtual target for needle alignment using the ureteroscope's location and orientation and the tower graphical user interface displays trajectory information. Upon gaining access to the kidney, the user will dilate the tract with the MONARCH™ Percutaneous Access Sheath and Dilator set.

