## 4.2 Subject exclusion criteria

Pre-Procedure Exclusion Criteria	
Subjects will be excluded from participating in this study if they meet any of the following criteria prior to initiation of the procedure:
 
 
1. Any medical or physical condition/limitation that would contraindicate a conventional ureteroscopy or PCNL in the supine position (e.g., atypical interposition of visceral organs (bowel, spleen, or liver))
 
2. Expected additional procedure, or participation in any clinical trial, from 30 days prior to the study procedure and throughout the duration of the study, which might impact this study's results
 
3. A solitary functioning kidney
 
4. Female subjects who are pregnant or nursing or those of child-bearing potential refusing a pregnancy test
 
5. Presence of ureteral impacted stones
 
6. Presence of ureteral obstruction
 
7. Complete staghorn stone
 
8. Presence of untreated urinary tract infection, urosepsis
 
9. Presence of a renal mass, which has not been investigated
 
10. Tumor in the probable access tract area
 
11. Potential malignant renal tumor
 
12. Subject has an electrically or magnetically activated implanted medical device
 
13. Significant pharmacological anticoagulant therapy or uncorrected bleeding diathesis
 
14. Inability to give consent
 

---	---

In addition, subjects will be excluded from participating in this study if any of the following exclusion criteria occur during the endoscopic procedure.

Intra-Procedure Exclusion Criteria	Any presenting condition discovered intra-procedurally that in the opinion of the investigator would make participating in this study not in the subject's best interest.
---	---

Criteria identified intraoperatively to justify patient exclusion, will be reviewed by the Sponsor, and considered for articulation directly in the protocol for future cases to ensure consistency in exclusion.

	PROTOCOL	Doc #:	104-016667-00
	Monarch Uro - Post-Operative Outcomes Study (2023-URO-0001)	Rev:	C
		Page:	24 of 52

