## **Secondary Endpoints**

Secondary endpoints in this study are:

- Stone free rate ( $\leq 4$  mm residual fragments, measured 30-days post-operative)
- Adverse events through 90-days post-operative, scored on the Clavien-Dindo scale
- Conversion to conventional treatment methods due to study device-related safety event

**Stone free rate:** This will be computed as the percentage of patients who are stone free assessed by CT at post-operative day 30. Stone free is defined as having  $\leq 4$  mm residual stones detected by CT. Patients who are found to not have any residual stone fragments at Day 1, will not undergo a second CT at post-operative Day 30, and will be presumed to be stone free at Day 30 for this calculation.

**Adverse events:** All adverse events will be captured up to post-operative Day 90, at which point the subject exits the study. See Section 7 below for description of how adverse events will be classified in this study. Adverse events will also be scored on the Clavien-Dindo scale. The Clavien-Dindo scale is system for grading the severity of postoperative complications (see Appendix III).

**Conversion to Conventional Treatment Methods Due to Study Device-Related Safety Event:** Number of procedures converted to conventional stone removal procedures (e.g., ureteroscopy or percutaneous nephrolithotomy) due to the occurrence of a study device-related safety event. A qualifying safety event, is a study device-related adverse event (see Section 7.1 below) that occurs during the study procedure, which prompts the physician to abort the study procedure, and pursue a conventional stone removal procedure. The conventional stone removal procedure need not occur within the same procedure. By contrast, conversion due to non-safety related device malfunction (e.g., unrecoverable fault observed from the ureteroscope robotic driver) will be captured separately, but will not count towards this endpoint. Similarly, conversion due to factors not related to the study device, but rather due to the patient's pre-existing condition (e.g., subject was not able to accommodate a ureteral access sheath during cystoscopy) will be documented as screen failures.

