### 8.3 Analysis Sets

The summary of all performance and safety endpoints will be performed on the set of subjects in whom the MONARCH™ Platform, Urology is utilized during the surgical procedure.

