## 8.2 Disposition of Study Subjects

Subject disposition will be summarized in total using counts and percentages. The number and percentage of subjects in the FAS who completed and discontinued will be tabulated along with the specific reasons for discontinuation.

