## 8.10 Handling of Missing Data

All summaries will be performed only on subjects undergoing the scheduled procedure and only observed data will be summarized. There will be no imputation of data for early terminated subjects or for missing data within the database.

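### Cases that start but stop before the ureteroscope is introduced are missing from the completion denominator, the completed/discontinued table and the adverse event summaries; the status of cases stopped later is unreconciled

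*SAP*

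**What the plan says.** SAP 6 sets one population for everything: "The summary of all performance and safety endpoints will be performed on the set of subjects in whom the MONARCH™ system is utilized". It then makes this operational: "This will be labeled as the Full Analysis Set (FAS) and will be identified by having a time recorded in the" ureteroscope-introduction field of the ureteroscopy and percutaneous access eCRF. Protocol 8.3 describes the set as those "in whom the MONARCH™ Platform, Urology is utilized during the surgical procedure", with no timestamp rule.

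Other sections build on this set or use different wording:

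- SAP 8.2: "The number and percentage of subjects in the FAS who completed and discontinued will be tabulated".
- SAP 8.10: "All summaries will be performed only on subjects undergoing the scheduled procedure".
- SAP 8.12 plans no sensitivity analysis.

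Protocol 3.2 lists retrograde access as the first component of the study procedure: the user reaches the kidney by cystoscopy and "places a ureteral access sheath to maintain access to the kidney". The ureteroscope follows, and percutaneous puncture comes after that. The first milestone of the primary endpoint (Protocol 3.1, SAP 8.5) requires safe access by both routes.

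On cases that stop, Protocol 5 makes enrolled subjects without the study procedure screen failures, but still collects their procedure-visit data and the reason. For conversions caused by the patient's pre-existing condition, Protocol 6 gives an example and a rule: "subject was not able to accommodate a ureteral access sheath during cystoscopy) will be documented as screen failures". Protocol 4.2 adds an intra-procedure criterion that rests on investigator opinion: "subjects will be excluded from participating in this study if any of the following exclusion criteria occur during the endoscopic procedure".

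**The concern.** The primary result is a single proportion with an exact interval and no comparator, so its meaning depends heavily on who is in the denominator. Here, entry to the denominator requires that an early step of the procedure has already succeeded. A subject in whom the access sheath cannot be placed, or whose case ends on a robot fault during device setup, has not completed the procedure but is not counted as a non-completion.

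The same gate applies to safety. Protocol 7.1 lists urethral false passage and ureteral injury from retrograde access among known procedure-related or anesthesia-related events. If such an injury ends the case before the ureteroscope goes in, it appears in no summary by system organ class, relatedness, seriousness or Clavien-Dindo grade.

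For cases stopped after introduction, the two documents label the same subject differently. The person who judges whether a conversion was needed also judges the intra-procedure exclusion. The analysis set should not be left open to interpretation at that point.

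**Working it through.** **Step 1: who is in the FAS, by the point at which the case stops.**

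| Case stops | Ureteroscope time? | Protocol label | FAS (SAP 6) |
|---|---|---|---|
| At cystoscopy or sheath placement, patient factor | No | Screen failure (Protocol 6) | Out |
| At device setup, before introduction | No | Study procedure not undergone: screen failure (Protocol 5) | Out |
| After introduction, robot malfunction with conversion | Yes | Primary endpoint failure (Protocol 6, SAP 8.5) | In |
| After introduction, percutaneous access fails or causes harm | Yes | Treated subject | In |
| After introduction, pre-existing or presenting condition | Yes | Screen failure or excluded (Protocol 6, 4.2) | In |

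The first two rows are the gap. The last row is the conflict. SAP 8.10 adds a third population phrase, not defined anywhere and not tied to the timestamp.

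**Step 2: effect on the completion rate.** There is no figure in the plan to reproduce: the sample size was not derived from a calculation. Let n be the FAS size, s the completions in it, and k the started cases with no ureteroscope time. The FAS rate is s/n. If the k cases are counted as not completed, the rate is s/(n+k). The difference is s/n − s/(n+k) = (s/n) × k/(n+k).

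Inputs: the planned maximum is 60 (SAP 7), and SAP 1.2 says enrollment stopped below that without giving the number. The values n = 20 and n = 60, 95% completion and k = 1, 3 or 6 are assumptions. Intervals are exact (Clopper-Pearson) 95%.

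| FAS | k | Rate with the k cases counted | Drop in points |
|---|---|---|---|
| 57/60 = 95.0% (86.1–99.0) | 1 | 57/61 = 93.4% (84.1–98.2) | 1.6 |
| | 3 | 57/63 = 90.5% (80.4–96.4) | 4.5 |
| | 6 | 57/66 = 86.4% (75.7–93.6) | 8.6 |
| 19/20 = 95.0% (75.1–99.9) | 1 | 19/21 = 90.5% (69.6–98.8) | 4.5 |
| | 3 | 19/23 = 82.6% (61.2–95.0) | 12.4 |
| | 6 | 19/26 = 73.1% (52.2–88.4) | 21.9 |

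With FAS completion varied from 90% to 100%, the drop runs from 1.5 points (n = 60, k = 1) to 23.1 points (n = 20, k = 6). With k = 0 it is zero.

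**Step 3: effect on safety.** Suppose three cases stop before introduction, one of them because of an access injury, and no such injury occurs in the FAS. The tables show 0/20 or 0/60. Counted on everyone started, it is 1/23 = 4.3% or 1/63 = 1.6%.

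**The case against.** A set defined by device use is a recognised choice in a single-arm descriptive study with no hypothesis, and Protocol 8.3 specified it in advance. The access that precedes the timestamp uses conventional cystoscopy and a third-party sheath. Protocol 3.1 lists cystoscopy data under a pre-procedure heading, although Protocol 3.2 lists retrograde access as a component of the procedure. Protocol 6 deliberately separates patient factors from device performance, and counting a patient whose anatomy will not take a sheath as a device failure would mix the two. This stands, and it is why the FAS should remain the primary set. It does not justify leaving these cases out of safety and disposition summaries, and it does not cover a robot fault at device setup.

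The record is also not lost. Adverse events are collected from consent (Protocol 7.1), and all eCRF data are listed for all subjects (SAP 8.1). This stands too, but a listing gives no rate and no denominator. SAP 8.2 opens by saying that disposition is summarized in total. Only the completed/discontinued counts are tied to the FAS.

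A reader might go further and infer that all access-stage harms vanish from the tables, or that the retrograde part of the first milestone cannot fail. Neither follows. Percutaneous access comes after introduction, so its failures and harms stay in the FAS. The ureteroscope must still be navigated to the kidney after it is introduced, and a failure there counts. Harms at cystoscopy or sheath placement are also tabulated if the ureteroscope is later introduced.

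**Conclusion.** The gap is real but limited to cases that start and stop before ureteroscope introduction. These are outside the completion denominator, the completed/discontinued table and all adverse event and Clavien-Dindo summaries, and no sensitivity analysis shows their effect.

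The size depends on a count that the documents do not give. At an assumed 95% FAS completion, one case is worth about 1.6 points at n = 60 and 4.5 at n = 20; three are worth about 4.5 and 12.4. Because enrollment stopped below 60, a given number of cases weighs somewhat more than the n = 60 figures show. It would be tempting to say that completion is overstated, but that holds only if such cases occurred.

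For subjects stopped after introduction, it would be tempting to say that they are removed from the analysis. No section says so: SAP 6 keeps anyone with a timestamp, while Protocol 4.2 and 6 may label the same subject excluded or a screen failure. SAP 8.10 uses different population wording within a missing-data section and does not define a second set. This is an unreconciled conflict, not a stated removal. The sections must be brought into line before the denominator is fixed.

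**What to change.** Keep the FAS as the pre-specified primary set and make these additions to the SAP:

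1. Define an Attempted-Procedure Set: every subject with a recorded cystoscope-introduction time on the pre-procedure setup eCRF. SAP 8.7 already uses this field for procedure duration. List separately, with the reason, any case stopped at device setup without that time.
2. Summarise adverse events and disposition on this set, with reasons for stopping.
3. Show a supplementary completion rate with an exact 95% interval on this set beside the FAS rate. Count cases that did not reach introduction as not completed, and separate patient-factor from device-factor reasons.
4. State that a subject with a ureteroscope time stays in the FAS whatever screen-failure or intra-procedure-exclusion label is applied, and reconcile Protocol 4.2 and 6 with this.
5. Align the population wording of SAP 8.10 with SAP 6.

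No new data are needed, because procedure-visit data and reasons are already collected for screen failures (Protocol 5). The cost is SAP text, one more table column and a supplementary rate that may look slightly less favourable. Aligning Protocol 6 may need a protocol clarification.
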